6.6.2. Rheumatic Disease History

Rheumatic disease history will be coded using the Medical Dictionary for Regulatory Activities (MedDRA) Version 23.0 or higher available later version. The number and percentage of subjects with any Rheumatic disease history will be summarized overall and for each system organ class. Percentages will be calculated based on number of subjects in the safety population.

Rheumatic disease history will be listed by condition/surgery with start and stop date.

6.7. Inclusion and Exclusion Criteria

The details of the inclusion and exclusion criteria can be found in [sections 4.1.1](#) and [4.1.2](#) of the protocol. List of inclusion criteria not met, and exclusion criteria met will be listed for all enrolled subjects.

7. Treatments and Medications

7.1. Prior and Concomitant Medications

A prior medication is defined as any medication that is taken within a month prior to screening visit and stop date prior to the first dose of study drug. A concomitant medication is defined as any medication taken at randomization and which continue to be taken during the study and medications started during the study that has a stop date on or after the date of first dose of study drug.

If the stop date is partially/completely missing, then the question on the eCRF; “If stop date is unknown, was this drug stopped before the first administration of study drug?” will be used for classification of the medication. If the answer is “Yes” then the medication will be classed as prior medication and if the answer is “No” then the medication will be classed as concomitant medication.

If the stop date is completely missing and medication is ‘ongoing’ then the medication will be classed as concomitant medication.

The total number of prior and/or concomitant medications and the number and percentages of subjects with at least one prior and/or concomitant medication will be summarized by treatment arm and listed by drug class (Anatomical Therapeutic Chemical (ATC) level 4) and preferred term. All summaries will be performed using the safety population.

A rescue medication is defined as medications with the indication rheumatoid arthritis started after the administration of the first dose of study drug unless allowed by Protocol at any time during the study and until the additional safety follow-up visit at Week 26. Rituximab given as a re-dosing as per the applicable Prescribing Information/SmPC at the time of patient treatment should not be considered as rescue medication. The total number of rescue medications and the number and percentages of subjects with at least one rescue medication will be summarized by treatment arm and listed by drug class (Anatomical Therapeutic Chemical (ATC) level 4) and preferred term. All summaries will be performed using the safety population.

7.2. Study Treatments

The study treatments (DRL_RI or US-rituximab/EU-rituximab) solution for infusion will be prepared by unblinded pharmacist designated as site team member in this study and will be administered two 1000 mg IV infusions separated by 2 weeks on Day 1 and Day 15. Subject will be pre-medicated with an antipyretic and an antihistamine before each infusion of rituximab. All subjects should also receive pre-medication with 100 mg IV methylprednisolone or its equivalent to be completed at least 30 minutes prior to rituximab infusions to decrease the incidence and severity of acute IRRs.

Below instructions should be followed in consolidation with the local product labelling if it differs from these instructions.

First infusion (Day 1): Initiate infusion at a rate of 50 mg/hour. In the absence of infusion toxicity increase infusion rate by 50 mg/hour increments at 30-minute intervals, to a maximum of 400 mg/hour.

Second infusion (Day 15): Initiate infusion at a rate of 100 mg/hour. In the absence of infusion toxicity, increase rate by 100 mg/hour increments at 30-minute intervals, to maximum of 400 mg/hour.

Subjects should be closely monitored post dose for at least 1-hour for the onset of IRRs. Subjects who develop evidence of severe reactions, especially severe dyspnea, bronchospasm, or hypoxia should have the infusion interrupted immediately. In all subjects, the infusion should not be restarted until complete resolution of all symptoms, and normalization of laboratory values. At this time, the infusion can be initially resumed at not more than one-half the previous rate. If the same severe reactions occur for a second time, the decision to stop the treatment should be seriously considered on a case by case basis.

Mild to moderate IRRs usually respond to a reduction in the rate of infusion. The infusion rate may be increased upon improvement of symptoms.

7.2.1. Treatment Compliance and Modifications

The number and percentage of subject with dose administered will be summarized on Day 1 and Day 15. The number and percentage of subjects with dose interruption with reason for interruption will be presented by visit. In addition, descriptive statistics for the total dose administered, and percentage of dose administered will be summarized by treatment arm. Summaries will be based on the safety population.

Percentage of dose received will be estimated based on the proportion of total dose administrated.

Dose received (%) = 100 * (total dose administered / total plan dose).

A listing will be provided for the safety population showing the details of study drug administration and pre-medication.

8. Immunogenicity Analysis

8.1. Analysis of Immunogenicity Endpoints

Blood samples for detection of ADA (including NAb) will be collected prior to initiation of the infusion (preferably within 30 minutes before initiation of the infusion) of study treatment on Day 1 and Day 15 and then on visits at Weeks 4, 8, and 12 (EOS/ET).

Summary statistics (frequency and percentage) by treatment arm and overall will be provided for the percent of subject with ADA formation at Day 1 and Day 15, and at weeks 4, 8, 12 (EOS/ET) visit. A subject is considered as ADA positive during the study if the subjects had at least one ADA positive sample otherwise the subject is regarded as ADA negative. Note this will also include any unscheduled visits during the study period.

Additionally, for subjects who are ADA positive at baseline, a shift table per treatment arm will be generated. The shift table includes numbers in each class (decreased, stable, and increased) as well as percentages relative to the number of ADA positive subjects with an available evaluation at the specific visit.

Subjects will be classified at each visit post baseline as:

- Decreased: If ADA titer at post-baseline visit decreases to a lower titer than that observed at baseline. Subjects with positive ADA at baseline in whom a titer is not detectable or non-evaluable at a corresponding post-baseline visit is decreased if the ADA turn negative.
- Stable: If ADA titer equal to that at baseline.
- Increased: If ADA titer increasing to a higher titer than that observed at baseline. Subjects with Negative ADA at baseline in whom a titer is not detectable or non-evaluable at a corresponding post-baseline visit is increased if the ADA turn positive.

The titer and the concentration of confirmed positive results will be reported. In addition, confirmed positive ADA samples will be analyzed for their neutralization potential in a neutralizing antibody (NAb) assay.

The incidence of ADA positive subjects and subjects with NAb will be summarized by treatment arms, by visit and overall. Antibody titers will be summarized by median and quartiles by treatment arm and visit.

A listing of immunogenicity data (including titer, concentration, ADA and Nab status) will be provided.

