Continuous data will be described using descriptive statistics (i.e. n, mean, standard deviation [SD], median, quartiles, minimum, and maximum). Categorical data will be described using the count and percentage in each category. For the summary statistics of all numerical variables unless otherwise specified, minimum and maximum will be displayed to the same level of precision as reported. Mean and median will be displayed to one level of precision greater than the data collected. Standard deviation will be displayed to two levels of precision greater than the data collected.

When count data are presented, the percentage will be suppressed when the count is zero in order to draw attention to the non-zero counts. A row denoted “Missing” will be included in count tabulations where specified on the shells to account for missing values. The denominator for all percentages will be the number of subjects within the analysis population of interest, unless otherwise specified. Percentages will be presented to one decimal place.

For Time Matched Rituximab Concentrations (TMRC) sample, concentration below the lower limit of quantification (BLLOQ) will be converted to '0' for the purpose of quantitative summaries, but will be presented as recorded, i.e. BLLOQ in listings.

Data will be displayed in all listings sorted by subject number and visit, if applicable. Listings will include all visits including unscheduled visits.

"No data available for this report" will be presented when there are no data available to report.

Unless otherwise specified, baseline will be defined as the last non-missing value collected before the first study drug administration. Study day is defined as:

- Visit/examination date – date of first study drug administration when date is prior to the date of first study drug administration (day 1).
- Visit/examination date – date of first study drug administration + 1 when date is on or after day 1.

For summaries by visit, if multiple records fall on the same visit and timepoint, then the record which is the earliest value will be chosen.

Unscheduled results will not be summarized but will be listed, unless otherwise specified. Post baseline summaries will include all values collected after the date of first study drug administration.

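### The overall by-arm ADA incidence mixes pre-existing with new antibody, and no listed table clearly reports treatment-induced ADA

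*SAP*

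**What the plan says.** SAP 8.1 defines the study-level outcome as follows: "A subject is considered as ADA positive during the study if the subjects had at least one ADA positive sample". Unscheduled samples count as well. The by-visit summary is of the "percent of subject with ADA formation at Day 1 and Day 15" and at the later visits, so the pre-dose Day 1 sample is reported as antibody formation. The overall result is then set out: "The incidence of ADA positive subjects and subjects with NAb will be summarized by treatment arms, by visit and overall". No subject-level rule is written for NAb.

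The one analysis that uses baseline status is a shift analysis: "for subjects who are ADA positive at baseline, a shift table per treatment arm will be generated". Its percentages are "percentages relative to the number of ADA positive subjects with an available evaluation at the specific visit". Its *Increased* class nevertheless covers subjects who were not positive at baseline: "Subjects with Negative ADA at baseline in whom a titer is not detectable or non-evaluable at a corresponding post-baseline visit is increased", provided they turn ADA positive.

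SAP section 4 gives the general conventions: "Unless otherwise specified, baseline will be defined as the last non-missing value collected before the first study drug administration", and "Post baseline summaries will include all values collected after the date of first study drug administration".

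The table list in SAP 12.2 has ADA and NAb by visit and overall (14.2.2.1), titer by visit (14.2.2.2) and the shift in subjects positive at baseline (14.2.2.3). Each has an A version for Estimand 1. Listing 16.2.6.1 gives ADA, NAb and titer by subject.

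**The concern.** Protocol 1.1.3 frames the trial around whether safety and immunogenicity change after a single transition from the reference product. Antibody already present before the first study infusion cannot be such a change. Protocol 4.1.1 requires at least one earlier full rituximab course, and baseline ADA is not an exclusion, so some subjects will plausibly be positive on Day 1.

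Under the written rule these subjects count as positive in the overall row of their arm. This has three consequences:

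- The relative contrast between arms is diluted, because a similar number of pre-existing positives is added to both.
- Noise is added. Randomization balances baseline positives only in expectation, and it is stratified by region only (SAP 4.2).
- The quantity that answers the transition question, the number of baseline negatives who convert in each arm, appears in no clearly defined table.

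The analysis is descriptive (Protocol 7.4.1 and 7.4.5), with no planned adjustment for baseline ADA, so readers will compare the arm percentages as printed. This does not depend on Estimand 1, which is exploratory and words its endpoint as development of ADA.

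**Working it through.** The SAP gives no figure to reproduce here; the point concerns a definition and a table list. The text comes first, then a numerical illustration.

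**What each planned output can show**

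| Output | New ADA by arm? |
|---|---|
| 14.2.2.1, visit rows | Net prevalence at each visit, Day 1 included; conversions and reversions cannot be separated |
| 14.2.2.1, overall row | Pre-existing and new ADA together |
| 14.2.2.2 | Titer levels, not converters |
| 14.2.2.3 | Introduction and title limit it to baseline positives; the *Increased* rule also names baseline negatives; the denominator does not say positive when |
| Listing 16.2.6.1 | Derivable by hand, not summarized |

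The *Increased* rule names converters only where the titer is undetectable or non-evaluable. Converters with a measured titer are not explicitly classified, though *Increased* is the likely intent.

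The section 4 convention on post-baseline summaries does not settle the matter. The overall row is not called post-baseline, and a baseline positive who stays positive would count even if Day 1 were excluded.

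**Inputs**

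- n = 70 per arm (Protocol 3.1.1).
- Baseline prevalence b: not given. Protocol 1.1.1.5 cites 11% positive on at least one visit in pooled trials, which is not a prevalence before re-treatment. The range 5% to 20% is assumed.
- New ADA among baseline negatives, r: assumed 3% (reference) versus 9% (DRL_RI), and 5% versus 15%. The true ratio is 3.0 in both cases.

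**1. Chance imbalance in baseline positives** (no assumption about r)

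Take two independent Binomial(70, b) counts. The SD of the difference in percentages is √(2b(1−b)/70). Four subjects is 4/70 = 5.7 points.

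| b | Expected positives per arm | SD (points) | P(arms differ by ≥ 4) |
|---|---|---|---|
| 5% | 3.5 | 3.7 | 17% |
| 11% | 7.7 | 5.3 | 34% |
| 20% | 14.0 | 6.8 | 46% |

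**2. What the overall row would read**

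Ever-positive: p = b + (1−b)r. At b = 11%, reference: 0.11 + 0.89×0.03 = 13.7%; DRL_RI: 0.11 + 0.89×0.09 = 19.0%.

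95% half-width: 1.96√[p₀(1−p₀)/m + p₁(1−p₁)/m], with m = 70 for ever-positive. For treatment-induced ADA, r replaces p and m = 70(1−b). The SAP plans no intervals; half-widths only show the noise.

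| b | r (ref vs DRL_RI) | Ever-positive (ref vs DRL_RI) | Difference (points) | Ratio | Half-width, ever-positive | Half-width, treatment-induced |
|---|---|---|---|---|---|---|
| 5% | 3% vs 9% | 7.85% vs 13.55% | 5.7 | 1.73 | 10.2 | 8.0 |
| 11% | 3% vs 9% | 13.7% vs 19.0% | 5.3 | 1.39 | 12.2 | 8.3 |
| 20% | 3% vs 9% | 22.4% vs 27.2% | 4.8 | 1.21 | 14.3 | 8.7 |
| 11% | 5% vs 15% | 15.45% vs 24.35% | 8.9 | 1.58 | 13.1 | 10.4 |

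The treatment-induced difference is 6.0 points for the first three lines and 10.0 for the last.

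**3. Restricting the overall row to post-dose samples**

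Let q be the assumed share of baseline positives who are positive again after dosing: p = bq + (1−b)r. With b = 11% and r = 3% versus 9%:

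| q | Row reads (ref vs DRL_RI) | Ratio | Pre-existing share of positives (ref / DRL_RI) |
|---|---|---|---|
| 0.5 | 8.2% vs 13.5% | 1.65 | 67% / 41% |
| 0.8 | 11.5% vs 16.8% | 1.47 | 77% / 52% |
| 1.0 | 13.7% vs 19.0% | 1.39 | 80% / 58% |

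**4. Masking, as a constructed example**

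Arm A has 3 baseline positives and 8 converters; Arm B has 8 and 3. Both overall rows read 11/70 = 15.7%. Treatment-induced rates are 8/67 = 11.9% and 3/62 = 4.8%.

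**The case against.** The strongest reply is that much is already visible. The Day 1 row by arm sits in the same table as the overall row, so a chance baseline imbalance could be seen, and the listing lets anyone derive converters. That stands, and it narrows the gap to one thing: aggregate rows cannot separate converters from subjects who revert.

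The *Increased* rule also suggests that converters were meant to be tabulated, and the table shells, which SAP section 4 mentions, are not in the documents. A baseline-negative row in a shell cannot be ruled out. But the introduction and title of the shift table say otherwise, so the text needs repair on either reading.

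The SAP does not say outright whether Day 1 counts in the overall row. Step 3 shows that mixing remains if it does not, though its size then depends on an assumed persistence.

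On size, every rate is assumed, and the SAP plans percentages rather than ratios. On the percentage scale the expected contrast barely moves (6.0 to 5.3 points). The remedy does not remove noise either: with 62 baseline negatives per arm and equal conversion of 5% or 6%, the arms would still differ by four or more converters 14% or 18% of the time. All of this is correct, and it limits the claim to dilution, added noise and an unreported quantity; bias is not shown.

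Finally, titers come from 2-fold dilutions (Protocol 6.2.2), so a one-step rise would count as boosted under the SAP's own *Increased* rule. That is a fair caution about the boosted row, but it does not touch the treatment-induced row.

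**Conclusion.** The concern holds and should be fixed; confidence is medium because the table shells are unseen. As written, the overall ADA row by arm combines pre-existing and new antibody. The same probably applies to NAb, for which no subject-level rule exists. No listed table clearly gives the number of converters by arm.

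Under the assumed rates, a threefold difference in new ADA would appear as a ratio of 1.2 to 1.7, and the overall row is noisier than the treatment-induced comparison. Limiting the row to post-dose samples does not cure this. The main loss is that the figure closest to the transition question goes unreported. Neither measure would resolve a 6-point difference at this sample size.

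**What to change.** **(a) Incidence tables.** In SAP 8.1 and Tables 14.2.2.1 and 14.2.2.1A, add by-arm rows using the SAP's existing baseline definition:

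- Treatment-induced ADA: baseline negative with at least one positive post-dose sample, unscheduled included. Denominator: baseline negatives with a post-dose result.
- Treatment-boosted ADA: baseline positives meeting the existing *Increased* titer rule. Denominator: baseline positives with a post-dose result.
- Not classifiable: no baseline result, since the immunogenicity population (SAP 4.3.2) does not require one.

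Base the between-arm reading of new ADA on the treatment-induced row. For NAb, write the subject-level rule and add a treatment-induced row, counting ADA-negative samples as NAb negative because only confirmed ADA positives are tested.

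**(b) Ever-positive row.** Keep it as supporting, labelled as including pre-existing ADA, and state whether Day 1 counts.

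**(c) Shift tables.** Align 14.2.2.3 and 14.2.2.3A with the class rules by using two blocks, each with its own denominator per visit: baseline positives (decreased, stable, increased) and baseline negatives (stayed negative, or converted with or without a measured titer).

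**Cost.** SAP wording and a few table rows. The data are already collected and listed, and the protocol endpoint is unchanged. The denominator falls to about 62 per arm at 11% baseline prevalence, and cells are small: about 2 versus 6 expected converters at 3% versus 9%, or 3 versus 9 at 5% versus 15%.

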3.1 Study Design

3.1.1 Description

This is a randomized, double-blind, parallel group, multicenter, Phase 3 transition study in subjects with active RA who are eligible for the subsequent treatment course with US-rituximab or EU-rituximab according to the clinical judgment of the investigator.

It is planned to randomize 140 subjects (70 per treatment arm) at approximately 50 sites in up to 7 countries (including, but not restricted to the United States).

A course of treatment with US-rituximab or EU-rituximab in RA consists of two 1000 mg IV infusions separated by 2 weeks. Subjects with RA who have received at least 1 full course comprising two 1000 mg infusions with either US-rituximab or EU-rituximab will be eligible for the study. The rituximab reference product (US-licensed rituximab [Rituxan] or EU-approved rituximab [Mabthera]) used should be the same in the prior and the randomized treatment course, respectively. Subjects having received the prior treatment course with reference products other than US-licensed rituximab (Rituxan) or EU-approved rituximab (Mabthera) will not be eligible for the study. Subjects should not be switched from the prior to the randomized treatment course from US-licensed to EU-approved reference product or vice versa.

Subjects will then be randomized by interactive web response system (IWRS) to receive either two 1000 mg infusions of DRL_RI (Arm A) or US-rituximab/EU-rituximab (Arm B) on Day 1 and Day 15. This will constitute the next course of rituximab treatment. Subjects randomized to Arm A will receive DRL_RI and subjects randomized to Arm B will continue to receive either US-rituximab or EU-rituximab.

The study will consist of a screening period (Days -14 to 0) and a double-blind period (Day 1 to Week 12). Subjects will attend a screening visit followed by visits at Weeks 0 (Day 1), 2, 4, 8, and 12 (end of study [EOS]) after randomization. An additional follow-up visit will be conducted at Week 26 to evaluate safety and to perform a serum pregnancy test in women of childbearing potential (WOCBP).

[figure not shown]
Subjects having signed the informed consent form (ICF) versions prior to the one introduced by this amendment need to re-consent to continue participating in the study after Week 12 through Week 26. If a subject does not re-consent for further study participation after Week 12, then his/her study data up to Week 12 will be collected and the subject will be discontinued from the study.

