7.4 Statistical Analysis Methodology

7.4.1 General Principles

The statistical analysis will be performed using SAS Version 9.4 or later.

The immunogenicity and safety data will be analyzed descriptively. All individual data as well as results of statistical analyses, whether explicitly discussed in the following sections or not, will be presented in individual subject data listings and statistical summary tables.

In general, continuous variables will be summarized using the following standard descriptive summary statistics: number of observations, arithmetic mean, standard deviation, minimum, median, and maximum. Categorical variables will be displayed by means of frequency tables including percentages.

Baseline is defined as the last non-missing pre-dose assessment. Overall summaries and analyses will be performed based on data pooled from all sites.

A SAP will be prepared and finalized before the clinical study database is closed.

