The study endpoints are the incidence of ADA (Anti-drug antibody), including titer and Nab (Neutralizing antibodies) primary safety endpoints of TEAEs (Treatment-emergent adverse events), SAEs (Serious adverse event), anaphylactic reactions, hypersensitivity reactions, infusion-related reactions (IRRs); and other safety endpoints of clinical laboratory parameters, vital signs, twelve-lead electrocardiogram (ECG) and physical examination. The subject's response to treatment will be assessed in accordance with usual clinical practice. Samples for the evaluation of ADA will be obtained before the administration of study treatment on Day 1 and Day 15. Additional samples for detection of ADA will be collected at Weeks 4, 8, and 12 (EOS/ET visit). Samples that are confirmed positive for ADA will be further tested for titer and Nab. Along with the immunogenicity sample, a time matched blood sample (approximately 5 mL) will be collected for the estimation of rituximab concentration. The evaluation of the samples will be performed to interpret safety and/or immunogenicity data appropriately, if needed.

The Schedule of Events is presented in [Appendix 12.1](#) and the study design overview is illustrated in [Figure 1](#) below.

Figure1: Study Design Overview

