4.3.2. Immunogenicity population

Immunogenicity population will include all subjects with at least one post dose ADA assessment result available.

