8.3. Analysis of Exploratory Endpoints

Possible intercurrent events (IcEvs) in this study are presented in [Table 2](#).

Table 2: Intercurrent events

Label	Intercurrent Event
IcEv1 (Death)	Death due to any cause
IcEv2 (Prohibited therapy)	Use of prohibited therapy that interferes with the evaluation of immunogenicity
IcEv3 (Missed/Discontinuation of IMP)	Missed/Discontinuation of IMP without receiving the second infusion as scheduled at Day 15 due to any reasons
IcEv4 (COVID-19/SARS-CoV-2 infection)	Incidence of COVID-19/SARS-CoV-2 infection after infusion.

Attributes for the immunogenicity and safety estimands with strategies for handling IcEvs are presented in [Table 3](#). Safety estimands are presented here together with the immunogenicity estimands for ease of reference to estimands.

Table 3: Immunogenicity and Safety Estimand

Estimand Label	Estimand 1 (Immunogenicity)
Estimand Description	Immunogenicity will be evaluated using incidence of positive ADA including Nab in subjects with active RA who are currently in treatment with US-rituximab or EU-rituximab and are eligible for the subsequent treatment course with US-rituximab or EU-rituximab. The development of ADA is measured while on study over up to 12 weeks or until death or use of prohibited therapies with impacts on immunogenicity assessments whichever is earliest, regardless of treatment discontinuation due to any other reasons.
Target Population	Subjects with active RA who are eligible for the subsequent treatment course with US-rituximab or EU-rituximab and would meet other study entry criteria and receive at least 1 dose of study treatment
Endpoint	Development of ADA, including titer and NAb
Treatment Conditions	Test: two 1000 mg infusions of DRL_RI Reference: two 1000 mg infusions of US-rituximab/EU-rituximab
Population-Level Summary	Incidence of ADA, including titer and NAb
Intercurrent Event (IcEv) Strategy	
IcEv1 (Death)	While-on-treatment strategy (measurements of the endpoint up until the time of the intercurrent event)
IcEv2 (Prohibited therapy)	While-on-treatment strategy
IcEv3 (Missed/Discontinuation of IMP)	Treatment policy strategy
IcEv4 (COVID-19/SARS-CoV-2 infection)	Treatment policy strategy

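### SAP 8.1 counts every subject without a positive sample as ADA negative, however few post-dose samples exist, so incomplete sampling can only lower the overall ADA/NAb incidence and goes unreported

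*SAP*

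**What the plan says.** Four post-dose ADA samples are scheduled: Day 15 before the second infusion, and Weeks 4, 8 and 12 (SAP 3.1 and 8.1). One is enough to enter the analysis. SAP 4.3.2: "Immunogenicity population will include all subjects with at least one post dose ADA assessment result available".

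SAP 8.1 then sets overall status. A subject is ADA positive during the study "if the subjects had at least one ADA positive sample otherwise the subject is regarded as ADA negative". Unscheduled samples count. The rule sets no minimum number of samples, requires no late sample and has no category for subjects who cannot be classified.

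On denominators, SAP section 4 says: "The denominator for all percentages will be the number of subjects within the analysis population of interest, unless otherwise specified". A row for missing data "will be included in count tabulations where specified on the shells to account for missing values"; the shells are not in the documents. SAP 8.1 names an available-evaluation denominator only for the shift table of subjects positive at baseline.

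The main endpoint keeps all samples to Week 12 whatever other therapy is used (SAP 3.2). Exploratory Estimand 1 does not. For death, SAP Table 3 specifies: "While-on-treatment strategy (measurements of the endpoint up until the time of the intercurrent event"). It names the same strategy for prohibited therapy, which Table 2 limits to therapy interfering with the immunogenicity evaluation. SAP 12.2 nevertheless places Tables 14.2.2.1A to 14.2.2.3A on the same Immunogenicity Population as the main tables.

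**The concern.** Absence of a positive sample means something different in a subject tested four times through Week 12 and in one tested once, before the second infusion. The rule gives both the same label. The error runs one way: an unobserved sample can hide a positive but cannot create one. NAb is affected too, because only confirmed ADA-positive samples go on to the NAb assay.

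ADA incidence is the study's immunogenicity endpoint, and Protocol 7.4.1 states: "The immunogenicity and safety data will be analyzed descriptively". The tabulated percentages are therefore the result, with no model or test behind them that handles missing data. If one arm loses more samples than the other, it will look less immunogenic for that reason alone, and the overall figure will not show it.

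In Estimand 1, a subject whose post-dose samples all follow interfering prohibited therapy has no usable post-dose sample left. The population is unchanged, so with a negative Day 1 sample that subject can be counted as negative in Table 14.2.2.1A on no post-dose evidence.

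**Working it through.** **Inputs.** The arm size is 70 (Protocol 3.1.1). The only background antibody rate in the documents is 11% of subjects positive on at least one visit (Protocol 1.1.1.5), used here for illustration. The sample-size sections are blacked out, so the plan offers no incidence or dropout figure to reproduce, and none is needed. Missingness, detection probability and all counts below are assumptions.

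**Average bias.** Let p be the true ever-positive rate, f the share of subjects incompletely sampled, and s the chance that a true positive among them is caught in the samples that exist.

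- Reported incidence = p × [(1 − f) + f × s]
- Loss = p × f × (1 − s), which is never negative

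| p | f | s | Loss (points) | Subjects per 70 |
|---|---|---|---|---|
| 11% | 5% | 0.75 | 0.14 | 0.10 |
| 11% | 10% | 0.50 | 0.55 | 0.38 |
| 11% | 20% | 0 | 2.20 | 1.54 |

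Over the same ranges of f and s, the loss is 0.06 to 1.0 points at p = 5% and 0.25 to 4.0 points at p = 20%. The relative loss is f × (1 − s), or 1.2% to 20%.

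**Between arms.** Take p = 11% in both arms and s = 0, with 20% incomplete in one arm and 5% in the other. The spurious difference is 2.20 − 0.55 = 1.65 points.

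**What the single percentage hides.** Take 70 subjects, 8 of them positive, and k incompletely sampled subjects without a positive.

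| k | SAP rule | Incomplete excluded | Incomplete all positive |
|---|---|---|---|
| 4 | 8/70 = 11.4% | 8/66 = 12.1% | 12/70 = 17.1% |
| 7 | 8/70 = 11.4% | 8/63 = 12.7% | 15/70 = 21.4% |
| 14 | 8/70 = 11.4% | 8/56 = 14.3% | 22/70 = 31.4% |

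The SAP reports 11.4% in all three cases. The exact 95% interval for 8/70 is 5.1% to 21.3%, so the average bias is small against sampling error.

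**Does exclusion solve it?** No. Early positives stay in while incompletely followed negatives leave, so the percentage is biased upward. Suppose 8 of 70 are truly positive (11.4%) and 7 subjects are incomplete, with 0.8 expected positives among them. If half are caught:

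- SAP rule: (8 − 0.4)/70 = 7.6/70 = 10.9%
- Exclusion: 7.6/(70 − 6.6) = 7.6/63.4 = 12.0%

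The two errors are about equal and opposite. With 75% caught, the SAP rule gives 7.8/70 = 11.1% and exclusion gives 7.8/63.6 = 12.3%, so exclusion is the worse of the two.

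**The case against.** The plan has real safeguards. Subjects who discontinue are asked to an EOS/ET visit that includes an ADA sample. Those who stop treatment only may continue visits. ADA and NAb are summarised by visit and listed by subject, and visits missed for COVID-19 are tabulated. A missing-data row may exist in the unseen shells. Estimand 1 is exploratory, its main counterpart keeps all samples, and showing both tables makes the effect of truncation visible. A while-on-treatment strategy is legitimate, and the protocol describes discretionary rescue after Week 12, when ADA sampling has ended, so few subjects may be truncated.

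All of this limits the size of the problem, but none of it changes a subject's overall status. The by-visit tables use the whole population unless the shells say otherwise. The EOS/ET visit shares the Week 12 label, so an early termination sample could be tabulated as Week 12. The listing leaves the count of incompletely sampled subjects to the reader.

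Two stronger readings are tempting and are not supported:

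- A reader might infer that truncation is driven by antibodies, so that the more immunogenic product looks better. Protocol 1.1.1.5 does call loss of drug level and efficacy a concern. It then reports that antibodies do not appear to affect B-cell depletion, clinical efficacy or re-treatment efficacy.
- A reader might infer a loss of up to 6 points, from 15% truncated and 40% of those converting. The documents give neither figure.

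**Conclusion.** The point holds as a reporting gap of moderate weight. The SAP's own wording reports unobserved follow-up as absence of antibodies. For subjects in the Immunogenicity Population, the effect on overall incidence can only be downward.

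The expected bias is about 0.1 to 2.2 points at 11% true incidence, assuming 5 to 20% incomplete sampling and detection of 0 to 75% of the positives among those subjects. That is at most about 1.5 subjects per arm of 70. The stronger reason to act is the undisclosed range, for example 11.4% to 21.4% with 7 incomplete subjects, and the possibility that it differs by arm. The arm comparison is distorted by any unequal missingness, whatever its cause.

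The Estimand 1 part affects exploratory tables only. The fault there is the unqualified negative label, not the choice of strategy.

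**What to change.** In SAP 8.1 and the overall ADA/NAb tables:

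- Add, by arm, a row for subjects with no positive sample who are incompletely sampled. Define this as no valid sample at or near Week 12, judged by actual sample date rather than visit label.
- Show the number with a valid sample at each visit and use it as the by-visit denominator.
- Report overall incidence under the present rule together with two further figures: incomplete subjects excluded, with a note that this biases upward, and incomplete subjects all counted as positive.
- In the Estimand 1 tables, require at least one usable post-dose sample before the intercurrent event before a subject may be counted as negative.

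A Kaplan-Meier estimate of time to first positive sample may be added as a sensitivity analysis only, stating that it assumes non-informative censoring.

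The cost is SAP wording, a few table rows and minor programming, with no new data collection. The downside is a wider and less favourable range around the headline percentage.
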